8.1.2. Complete Case Sensitivity Analysis of the Primary Efficacy Endpoint

If imputation of missing data is required, a complete case analysis will be performed in the ITT population. The complete case analysis will be exactly parallel to the planned primary efficacy analysis, except it will exclude any participants with missing average SUDS scores at Visit 3 (Treatment), using only observed responses. Descriptive summaries will be provided for the primary endpoint based on the complete-case data.

8.1.3. Sensitivity Analysis of the Primary Endpoint in the Per Protocol Population

A sensitivity analysis of the primary endpoint will be performed in the PP Population. The analysis will be exactly parallel to that described in Section 8.1.1 except that imputation will not be necessary. All subjects in the PP Population will have non-missing average SUDS scores at Visit 2 (Baseline) and Visit 3 (Treatment).

8.2. Secondary Efficacy Analysis

The secondary endpoint will be tested for the following hypothesis:

H₂₀: The proportion of CGI-I responders at Visit 3 (Treatment) does not differ between PH94B and placebo.

H₂₁: The proportion of CGI-I responders at Visit 3 (Treatment) does differ between PH94B and placebo.

The estimand for the secondary efficacy endpoint has the following components:

Attribute	Definition	
Treatment	The treatment of interest is PH94B, 3.2 μg administered as an intranasal solution (a 1.6 μg spray to each nostril per dose).	
Population	The population of interest is adult subjects with SAD as defined by the protocol inclusion and exclusion criteria.	
Variable of Interest	The variable of interest to be measured is the CGI-I score at Vis 3 (Treatment).	
Intercurrent Events	Intercurrent events are expected to be rare. Any intercurrent event that does occur will be handled using the treatment policy strategy, i.e., included in the treatment regimen under evaluation.	
Population Summary	The proportion of subjects with CGI-I scores of 1 or 2 for PH94B will be compared to placebo using a comparison of binomial proportions.	

8.2.1. Comparison of Binomial Proportions Analysis of the Secondary Endpoint

The proportion of CGI-I responders in each treatment arm will be computed as described in Section 6.1.7.3.

The PH94B and placebo proportions of CGI-I responders will be compared using a normal approximation (Wald) test for the difference between 2 binomial proportions. The proportion of responders in each treatment group, difference in proportions of responders between treatment groups, 95% CIs for the difference in proportions, and *P* value for the Wald test for equality of proportions will be presented.

[figure not shown]
Additionally, CGI-I scores will be summarized using frequencies and percentages by treatment group.

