13.1.4.3 Secondary Analyses

This secondary endpoint will be analyzed using a normal approximation test for the difference between 2 binomial proportions. The null hypothesis to be tested is that the population proportions are equal.

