3.5. Method of Assigning Subjects to Treatment Groups

Subjects who meet study entry criteria, and who complete the Visit 2 (Baseline) public speaking challenge with at least 1 SUDS score of 75 or higher will be randomly assigned in a 1:1 ratio to the PH94B or placebo treatment arms. The randomization schedule will be computer generated using a permuted block algorithm and will randomly allocate investigational product (IP) to randomization numbers. The randomization numbers will be assigned sequentially through a central interactive web response system (IWRS). Randomization will be stratified by study site; blocks will be allocated to sites by IWRS in real-time.

[figure not shown]
The randomization schedule will be prepared by before the start of the study. No one involved in the study performance will have access to the randomization schedule before official unblinding of treatment assignment. No subject will be randomized into this study more than once.

Each study site will be provided with a supply of blinded IP, each vial individually numbered with a unique alpha-numeric identification code. For Visit 2 (Baseline) and Visit 3 (Treatment), the IWRS system will provide a unique vial identification code indicating the study drug vial to be dispensed to the subject. The vial identification codes will be recorded in the drug dispensing record and the electronic case report form (eCRF).

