4.1. Introduction

Data processing, tabulation of descriptive statistics, calculation of inferential statistics, and graphical representations will primarily use SAS (release 9.4 or higher). If the use of other

software is warranted, the final statistical methodology report will detail what software was used for what purposes.

Unless otherwise stated, all continuous (quantitative) variable summaries will be presented by treatment group and include the number of subjects with non-missing values (n), mean, SD, minimum, first quartile (Q1), median, third quartile (Q3), and maximum.

Unless otherwise stated, all categorical (qualitative) variable summaries will be presented by treatment group and include the frequency and percentage of subjects who are in the particular category or each possible value. In general, the denominator for the percentage calculation will be based upon the total number of subjects in the relevant study population with non-missing values.

The minimum and maximum will be reported with the same degree of precision (i.e., the same number of decimal places) as the observed data. Measures of location (mean, median, Q1, and Q3) will be reported to 1 degree of precision more than the observed data and measures of spread (SD) will be reported to 2 degrees of precision more than the observed data.

Percentages <100% will be presented to 1 decimal place and percentages of 100% will be reported with no decimal place. Counts of zero will be presented without percentages.

Unless otherwise indicated, all statistical tests will be conducted at the 0.05 significance level using 2-tailed tests, and *P* values will be reported. Corresponding 95% confidence intervals (CIs) will be presented for statistical tests.

To control for the overall type I error rate, a fixed-sequence testing strategy will be used. If statistical significance is declared for the primary endpoint, formal hypothesis testing will be done for the secondary endpoint. If a non-significant *P* value is reached for the primary endpoint, *P* values for the secondary endpoint will be considered exploratory. The *P* values from the exploratory endpoints are not included in the fixed-sequence testing strategy and are included for informational purposes only. The planned sequence of hypothesis testing is detailed in Section 6.1.3.

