6.1.2. Adjustments for Covariates

Planned analysis of covariance (ANCOVA) analyses will adjust for analysis site (Section 6.1.6) and the baseline of the target endpoint by including them as terms in the model. The comparison of binomial proportions for the secondary endpoint will be presented overall and by strata.

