6.1.3. Multiple Comparisons

[figure not shown]
The type I error rate of $\alpha = 0.05$ will be maintained for the study by using a fixed-sequence testing strategy for the primary and secondary endpoints. Testing of the secondary endpoint will proceed only if the primary endpoint achieves statistical significance. No multiple comparisons adjustments will be made for the exploratory endpoints as the analyses are included for descriptive purposes only. All P values for each comparison will be provided in the summary tables for informational purposes.

The testing will be done in the following order:

1. Primary efficacy endpoint: difference in average SUDS score during the Visit 3 (Treatment) public speaking challenge versus the average SUDS score during the

AD-ST-33.06 Effective date: 12-Nov-2020

Version Final 1.0 | Date 28-Jun-2022 | AD-ST-33.06 Effective date: 12-Nov-2020 | Page 21 of 140

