6.1.6. Pooling of Sites

Analysis sites (pooled sites) will be created if sites have fewer than 6 randomized subjects. Sites will be ordered by the number of randomized subjects. The smallest study site will be combined with the next smallest study site. These 2 sites may be combined with the next smallest study site if the combined number of subjects remains less than 6. This process will be continued until this first pooled site has 6 or more randomized subjects. Once pooling is completed for the first pooled site, the pooled site and all unpooled sites will be reordered by the number of randomized subjects. If the new smallest site has fewer than 6 randomized subjects, the pooling will proceed again as described above to create a second pooled site, followed by reordering of pooled and unpooled sites by the number of randomized subjects. The process will repeat until the smallest site has 6 or more randomized subjects. If, in combining the 2 smallest sites, the resulting new analysis site becomes the largest study site (i.e., more subjects than present in the initial largest site), the combining of sites will be halted and not performed. The final determination of pooled sites will be made prior to database lock.

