8.1.1. ANCOVA Analysis of the Primary Endpoint

For each subject at each public speaking challenge, average SUDS scores and change from baseline (Visit 2 [Baseline] to Visit 3 [Treatment]) in average SUDS scores will be calculated as described in Section 6.1.7. Descriptive summaries of average SUDS scores and change from baseline in average SUDS scores will be provided for the primary endpoint based on the observed data.

An ANCOVA model will be used to test the null hypothesis that there is no difference in change from baseline average SUDS scores between PH94B- and placebo-treated subjects. Treatment group and analysis site will be included as factors and baseline average SUDS score as a covariate. The change from baseline LS means with standard error (SE), 95% CI for the LS means, *P* value for testing if the LS mean is 0, LS mean difference between treatment groups (PH94B minus placebo) with SE, 95% CI for the LS mean difference, and *P* value for testing if the treatment LS means are equal will be presented.

It is expected that all randomized study subjects will complete the Visit 3 (Treatment) assessments. If, for unanticipated reasons (intercurrent events), the fraction of subjects with missing change from baseline to Visit 3 (Treatment) average SUDS scores is greater than 0.05, change from baseline to Visit 3 (Treatment) average SUDS scores will be imputed using the fully conditional specification approach to multiple imputation as described in Section 6.1.4. If the fraction of missing change scores is ≤0.05, missing change from baseline to Visit 3 (Treatment) in average SUDS scores will be imputed with treatment group mean change scores.

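### The confirmatory CGI-I test leaves out site, the randomisation stratum; if response differs between sites the test is conservative and its confidence interval too wide

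*SAP*

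**What the plan says.** - **Randomisation (SAP 3.5; also protocol 9.5):** "Randomization will be stratified by study site; blocks will be allocated to sites by IWRS in real-time".
- **Primary model (SAP 8.1.1):** "Treatment group and analysis site will be included as factors and baseline average SUDS score as a covariate".
- **Position of CGI-I (SAP 6.1.3):** it is second and last in the fixed sequence. "Testing of the secondary endpoint will proceed only if the primary endpoint achieves statistical significance". SAP 4.1 sets the level: "all statistical tests will be conducted at the 0.05 significance level using 2-tailed tests".
- **CGI-I test (SAP 8.2.1):** responder proportions are "compared using a normal approximation (Wald) test for the difference between 2 binomial proportions", giving one difference, its CI and one P value. Protocol 13.1.4.3 agrees: "This secondary endpoint will be analyzed using a normal approximation test for the difference between 2 binomial proportions".
- **Strata (SAP 6.1.2):** "The comparison of binomial proportions for the secondary endpoint will be presented overall and by strata". No visible text combines the strata into one test or interval.
- **Small sites (SAP 6.1.6):** "Analysis sites (pooled sites) will be created if sites have fewer than 6 randomized subjects".

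**The concern.** Balancing the arms within sites removes between-site variation from the treatment difference. An analysis that includes site uses that gain; one that omits it still counts the between-site part as noise. The SAP includes site for the primary endpoint but not for the one other endpoint on which a formal claim can rest.

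Site differences are plausible here, although the documents do not quantify them. CGI-I is scored by the trained observer of each subject's speech (protocol 10.2.3 and 10.3.1.6), so scoring is local across 15 to 18 sites, and observers may differ in what they call much less anxious. At stake are some power and an interval wider than it needs to be.

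**Working it through.** **1. The plan's own figures.** No power is stated for CGI-I, and 208 subjects (104 per arm) were sized on SUDS. The one documented result for a test of this kind is the Phase 2 Z of 4.03 (protocol 5.2.2), from 34/45 v 17/46.

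- Unpooled: 0.3860 / √(0.7556×0.2444/45 + 0.3696×0.6304/46) = 0.3860 / 0.0958 = 4.03. This reproduces the figure.
- Pooled: 0.3860 / 0.1041 = 3.71. This does not.

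The Wald test is therefore taken as unpooled, as its name implies.

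**2. Mechanism.** The Wald variance is p₁(1−p₁)/n₁ + p₀(1−p₀)/n₀. With a common marginal rate p, n per arm and arms balanced within sites, the true variance is about (2/n)[p(1−p) − Var(site rates)]. The second term is what the test leaves out. In simulation at 37% in both arms and site logit SD 1.0, the mean Wald SE was 0.0663 and the true SD of the difference 0.0615. The effective critical value is 1.96 × 0.0663/0.0615 = 2.11, a two-sided level of about 0.035; the simulated level was 0.036.

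**3. Size of the effect.** Assumptions that are not in the documents:

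- 16 sites of 13, split 6 v 7 at random;
- PH94B response 56%, about half the Phase 2 difference (37 + 38.6/2 = 56.3). Placebo 37% is the Phase 2 rate;
- site intercepts normal on the logit scale, with marginal rates held fixed.

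There were 200,000 trials per scenario. CMH was run without continuity correction, and the Mantel-Haenszel risk difference used the Sato variance.

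| Site SD (logit) | Placebo rate, 10th–90th percentile of sites | Wald size | Wald CI width ÷ stratified | Power, Wald | Power, CMH | Change (points) |
|---|---|---|---|---|---|---|
| 0 | same at all sites | 0.053 | 1.00 | 79.4% | 78.5% | −0.9 |
| 0.5 | 23–52% | 0.048 | 1.02 | 80.2% | 80.8% | +0.6 |
| 0.8 | 16–60% | 0.042 | 1.06 | 81.0% | 83.5% | +2.5 |
| 1.0 | 13–65% | 0.036 | 1.09 | 81.4% | 85.4% | +4.0 |

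CMH size was 0.049–0.051 throughout. At SD 1.0 the mean CI widths were 0.264 (Wald) and 0.242 (stratified), a ratio of 1.09.

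**4. Sensitivity.**

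- Rates fixed at the average site instead of marginally (100,000 trials): the change is −1.0 / +0.7 / +3.4 / +5.5 points.
- A differently built simulation (40,000 trials, blocks of 4, 37% v 56.3%) gave Wald size 5.3 / 4.7 / 3.6 / 2.7% at SD 0 / 0.5 / 1.0 / 1.5, and CI ratios of 1.00 / 1.02 / 1.09 / 1.17. Power was Wald 80.5 / 81.0 / 82.8 / 84.0% against CMH 79.5 / 81.6 / 86.6 / 90.9%. Uneven sites of 6 to 20 gave the same pattern.
- No site effect, exact enumeration at 104 per arm: unpooled Wald size is 0.053–0.056 for rates 0.2–0.5, so it is slightly liberal.
- Phase 2 rates (75.6% v 37%): exact Wald power is 0.99996.

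**The case against.** The strongest reply is that the planned test is valid, prespecified consistently in both documents, and errs in the safe direction when sites differ. That stands: with site differences, type I error is at or below nominal, and a positive result would not be undermined.

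The size also rests on heterogeneity that nobody has shown. The challenge is meant to be uniform across sites, CGI-I compares a subject's second speech with the first, and the same observer attends both. This may limit site differences, though it does not remove differences in observer leniency. At SD 0.5 or below the effect is negligible, and at the Phase 2 rates it disappears. Those rates are a weak guide, however. They come from 91 women given 1.6 µg, and the amendment's stated reason is that the similar Phase 3 study missed its primary endpoint.

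The protocol's own ANCOVA text (13.1.4.2) names only baseline SUDS, so the contrast with the primary exists only within the SAP. That is correct, but the SAP is where the tests are defined.

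A stratified test might be hidden by redaction, or implied by SAP 6.1.2. This is unlikely. The synopsis, protocol 13.1.4.3 and 13.1.4.6.2, and SAP 8.2 and 8.2.1 all describe a simple comparison of two proportions, and presenting results by strata is a display.

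Finally, at SD 1.0 the stratified CI covered 94.4% and the Wald CI 96.3%, so a small part of the 9% width gap comes from the stratified interval being slightly short.

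**Conclusion.** The concern holds. The second confirmatory test omits the stratification factor that the design uses and the SAP's primary analysis includes. If sites differ, it is conservative and its interval too wide.

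Under the stated assumptions the cost is negligible at a site logit SD of 0.5. At 1.0 it is moderate: size 0.036, CI 9% wider, about 4 points of power. It matters when the true effect is well below Phase 2, where power is near 80%. The main uncertainty is site heterogeneity, on which the documents are silent. This is an efficiency gain worth taking before unblinding; it is not a threat to validity.

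**What to change.** - In SAP 8.2.1, make the confirmatory CGI-I test a CMH test stratified by the Section 6.1.6 analysis sites, without continuity correction. Report the Mantel-Haenszel common risk difference with a stratified 95% CI, and name the variance estimator (for example Sato).
- In SAP 6.1.2, define the strata and state that by-site results are descriptive, without P values. With about 13 subjects per site, a within-site Wald test is uninformative and can have zero estimated variance. Note this as an exception to the SAP 6.1.3 statement on reporting P values.
- Record the departure from protocol 13.1.4.3 and the synopsis in SAP Section 11 before database lock and unblinding.

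**Cost:** two section edits and one Section 11 entry. No new data are needed, and the pooled sites are already defined. The SAP needs revising anyway: it is written to protocol Version 3.0 and plans no interim analysis, while Amendment 3 adds one. The exploratory PGI-C and SUDS responder analyses refer back to 8.2.1 and would follow the change. The statistical price is about 1 point of power if sites truly do not differ.

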3.2. Sample Size and Power

The sample size calculation was based on the similarly designed Phase 2 randomized, double-blind, placebo-controlled clinical study of PH94B with the primary outcome variable of average subjective anxiety based on SUDS scores.

AD-ST-33.06 Effective date: 12-Nov-2020

Version Final 1.0 | Date 28-Jun-2022 | AD-ST-33.06 Effective date: 12-Nov-2020 | Page 14 of 140

Because this Phase 3 study will involve 15 to 18 sites

Based on these considerations, 208 subjects (104 in each arm) will be included in the study.

Figure 1 provides the power curve used to determine the sample size.

An estimated 400 subjects will be screened to randomize 208 subjects in a 1:1 manner to either PH94B or placebo.

[figure not shown]

3.3. **Study Population**

The study population consists of male or female subjects, 18 through 65 years of age, inclusive, with a current diagnosis of SAD and with no prior or current conditions that would increase risk of treatment or confound the results of the study.

3.4. **Treatments Administered**

Subjects will be randomized 1:1 to receive one of the treatments listed below at Visit 3 (Treatment).

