8.3. Exploratory Efficacy Analysis

All exploratory endpoints will be summarized, and P values will be included for descriptive purposes only.

[figure not shown]
The following analyses will be performed on the observed data for the ITT Population. All derived variables will be computed as described in Section 6.1.7.

1. The PH94B and placebo proportions of PGI-C responders will be compared using a parallel analysis to that described for the CGI-I endpoint (Section 8.2.1).

5. Proportion of SUDS responders (subjects with a ≥20-point improvement in average SUDS score from Visit 2 [Baseline] to Visit 3 [Treatment]) will be compared between the PH94B and placebo arms using a normal approximation test for a difference in binomial using a parallel analysis to that described for the CGI-I endpoint (Section 8.2.1).

6.

The primary and secondary endpoints will be summarized by subgroups of interest

Racial categories will be combined into larger categories should there be fewer than 5 subjects in a particular category within a treatment arm. Analyses will be performed on the observed data.

Subgroup Analyses of Primary Efficacy Endpoint

The primary efficacy endpoint of change in average SUDS scores from Visit 2 (Baseline) to Visit 3 (Treatment) will be compared between PH94B- and placebo-treated subjects

Subgroup analyses of the primary efficacy endpoint will be analogous to the ANCOVA analysis outlined in Section 8.1.1 but imputation will not be performed.

Subgroup Analyses of Secondary Efficacy Endpoint

The secondary efficacy endpoint of proportion of CGI-I responders will be compared between PH94B- and placebo-treated subjects within each of the subgroups listed above. Subgroup analyses will be compared using a normal approximation (Wald) test for the difference between 2 binomial proportions as described in Section 8.2.1.

9. Safety and Tolerability Analysis

Safety in this study will be evaluated based on data collected on AEs, clinical laboratory assessments, vital signs, 12-lead ECGs, suicidality, level of depression, and physical examinations including examination of the nasal passages.

All safety analysis reporting will be based on the Safety Population (as defined in Section 5). No formal statistical testing will be conducted for the safety analyses. Descriptive statistics will be used to evaluate safety data. Summaries will present data by treatment group and overall subjects. Listings will list safety data by treatment group and subject.

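### The Wald interval and test for CGI-I responders are carried into race subgroups as small as 5 per arm, where nominal 95% intervals usually cover too little and can have zero width

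*SAP*

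**What the plan says.** SAP 8.2.1 states that the CGI-I responder proportions will be "compared using a normal approximation (Wald) test for the difference between 2 binomial proportions". It reports the Wald P value and "95% CIs for the difference in proportions". No interval method is named beyond the Wald sentence, and the form of the variance is not written out.

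CGI-I response is the second of two confirmatory endpoints. SAP 6.1.3 says that the type I error rate of 0.05 "will be maintained for the study by using a fixed-sequence testing strategy for the primary and secondary endpoints", and SAP 4.1 says that "all statistical tests will be conducted at the 0.05 significance level using 2-tailed tests". SAP 3.2 plans that "208 subjects (104 in each arm) will be included in the study".

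The subgroup text that follows the exploratory analyses in SAP 8.3 (the contents list it as 8.4) says: "Subgroup analyses will be compared using a normal approximation (Wald) test for the difference between 2 binomial proportions as described in Section 8.2.1". The only visible size rule there is: "Racial categories will be combined into larger categories should there be fewer than 5 subjects in a particular category within a treatment arm". The PGI-C and SUDS responder analyses in 8.3 copy 8.2.1. SAP 6.1.2 adds that the secondary comparison will be shown by strata as well as overall.

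**The concern.** The unpooled variance is estimated from the two observed proportions, so it is smallest when those proportions are far apart or extreme. In large samples this hardly matters. In very small groups the interval becomes too short and the P value too small. If every subject or no subject responds in each arm, the estimated variance is zero. The interval then collapses to a point and the statistic is infinite or undefined. The visible text gives no rule for this case and no small-sample alternative.

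What is at stake is how subgroup results are read. SAP section 1 (Overview) foresees that these analyses may appear in study reports, submissions and manuscripts. A reader will take a 95% interval for a small race category at face value.

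**Working it through.** **Inputs.** 104 per arm (SAP 3.2); two-sided alpha 0.05 (SAP 4.1); smallest unmerged race category 5 per arm (SAP subgroup text); Phase 2 CGI-I responders 34/45 on PH94B and 17/46 on placebo, Z = 4.03 (protocol 5.2.2). These Phase 2 rates, 75.6% and 37%, are the only CGI-I responder rates in the documents. All other rates below are assumptions.

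**Step 1: which variance?** The difference is 34/45 - 17/46 = 0.7556 - 0.3696 = 0.3860.
- Unpooled: SE = √[p₁(1-p₁)/45 + p₂(1-p₂)/46] = 0.0958, so z = 4.03. This matches.
- Pooled, with p = 51/91 = 0.5604: SE = √[p(1-p)(1/45 + 1/46)] = 0.1041, so z = 3.71.
- With a continuity correction: 3.80 (unpooled) and 3.50 (pooled).

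Only the unpooled form gives the protocol's figure.

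**Step 2: why group size matters.** With n per arm in both arms, z²(Wald) = z²(score) / [1 - z²(score)/(2n)].
- n = 104, 52/104 v 38/104: score z = 1.959, and z²(Wald) = 3.839/(1 - 3.839/208) = 3.911, so Wald z = 1.978.
- n = 5, 4/5 v 1/5: score z² = 3.6, and z²(Wald) = 3.6/(1 - 0.36) = 5.625, so Wald z = 2.37. P is 0.018 by Wald and 0.058 by score. The Wald interval is 0.6 ± 1.96 × 0.253 = 0.10 to 1.10, which runs past the largest possible difference.

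**Step 3: small groups.** All outcomes of two independent binomials were enumerated. Coverage of the nominal 95% interval:

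| True rates | Wald, 5 per arm | Newcombe, 5 per arm | Wald, 6 per arm |
|---|---|---|---|
| 75.6% v 37% | 82.8% | 94.9% | 88.2% |
| 37% v 37% | 90.4% | 93.8% | 86.9% |
| 50% v 50% | 89.1% | 93.9% | 85.4% |
| 40% v 20% | 87.2% | 95.9% | 87.0% |
| 30% v 30% | 92.2% | 94.2% | 89.0% |
| 20% v 20% | 95.6% | 96.2% | 93.4% |

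Over all rate pairs from 20% to 80% with 5 per arm, Wald coverage runs from 78% to 96%, with median 88%.

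Null rejection rate of the Wald test at a common rate of 40%: 10.2% (5 per arm), 13.7% (6), 8.0% (8), 9.2% (10), 7.6% (20). The score z gives 6.2% and 6.3% at 5 and 6 per arm.

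Chance of zero width with 5 per arm is the product over arms of p⁵ + (1-p)⁵:
- Phase 2 rates: 0.2478 × 0.1062 = 2.6%.
- Both rates 20%: 0.328² = 10.8%.

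**Step 4: main test at 104 per arm.** For common rates of 20-80%, exact size is 5.22-5.78% for Wald and 4.47-5.26% for the score z. At 37% the figures are 5.33% and 5.21%. The two tests disagree only when the score P value lies between 0.0501 and 0.0520. At the Phase 2 rates the chance of such a table is about 0.002%. Wald interval coverage at this size is 94.4-95.2% for the pairs checked.

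**The case against.** A reader might infer from Step 4 that the confirmatory test fails to hold 5% alpha. The documents do not support that, for four reasons.
- The excess is 0.2-0.8 percentage points, and the score test also passes 5% at some rates.
- The calculation ignores sites. Randomisation is stratified by site (SAP 3.5), the test is unstratified, and site observers score the CGI-I (protocol 10.3.1.6), so real site differences would make the test conservative. In a simulation with 16 sites of 6-7 per arm and an assumed between-site SD of 0.12 in the responder rate, Wald size was 4.7-5.0% for rates of 37-50%. That removes the excess.
- CGI-I is tested formally only after SUDS succeeds, so study-wide error is touched only if the SUDS null is false and the CGI-I null is true.
- The protocol also specifies a normal approximation, and the SAP names its method in advance.

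A reader might also infer that small race groups will show spurious differences. A null rejection rate of about 10% means that about nine in ten such groups would show none.

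On the subgroups themselves, 5 per arm is the floor of a merging rule and not an expected size, the documents give no race distribution, and coverage depends on the rates. The subgroup list is not visible, so missing small-sample handling can be asserted only for the visible text. All of this stands, but it limits how often the problem arises. It does not make the stated method sound where the rule allows it. That the subgroups are descriptive does not rescue them either, because describing precision is what their intervals are for.

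**Conclusion.** The point holds for small groups. As written, the SAP permits responder comparisons with 5 subjects per arm using an interval that typically under-covers: 82.8% at the Phase 2 rates, 85-92% at most other pairs checked with 5-6 per arm, and near nominal at 20%/20%. The test there rejects a true null 10-14% of the time at a 40% common rate with 5-6 per arm. With 5 per arm, zero-width intervals arise in about 3% of cases at the Phase 2 rates and about 11% if both rates are 20%. No study alpha is at risk, so the fault is misstated precision. For the main analysis the issue is minor and alters the decision only for P values very close to 0.05.

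This rests on reading Wald as unpooled variance, on independent binomial outcomes with equal arms, and on the rates shown. If the strata in SAP 6.1.2 are sites, the same fault reaches groups of about 3 per arm, since SAP 6.1.6 asks for only 6 randomised subjects per analysis site. The visible text does not say what the strata are.

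**What to change.** For subgroup, by-strata and other small-group responder comparisons, specify Newcombe or Miettinen-Nurminen intervals, with an exact mid-P value or no P value where an arm has fewer than about 20 subjects. For consistency, use the score (null-variance) z-test and the same interval in SAP 8.2.1 and in the PGI-C and SUDS responder analyses of 8.3 that follow it. State the variance form explicitly, and say what the strata in 6.1.2 are. Make the change before unblinding.

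The cost is SAP wording and an option in the frequency procedure. The downside is slightly wider intervals and marginally larger P values.

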6.1.7.3. Clinical Global Impression Scale of Improvement (CGI-I)

[figure not shown]
The CGI-I is a clinician-rated instrument that measures the clinician's evaluation of change in subjects' overall improvement with treatment. Clinicians will respond to the following question:

"Please choose the response that best describes how anxious you felt the subject was during the second speech compared to how anxious they appeared in the first speech a week ago.

AD-ST-33.06 Effective date: 12-Nov-2020

Version Final 1.0 | Date 28-Jun-2022 | AD-ST-33.06 Effective date: 12-Nov-2020 | Page 24 of 140

[figure not shown]

• **Proportion of CGI-I Responders** = Proportion of subjects with a score of 1 (Very much less anxious) or 2 (Much less anxious) on the CGI-I at Visit 3 (Treatment).

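### The confirmatory CGI-I test is valid but leaves out baseline SUDS and site; adjusting for them could add a little precision, if they predict response

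*SAP*

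**What the plan says.** **Secondary test.** SAP 8.2.1 says the two proportions of CGI-I responders (score 1 or 2) will be "compared using a normal approximation (Wald) test for the difference between 2 binomial proportions". Protocol 13.1.4.3 agrees: the endpoint "will be analyzed using a normal approximation test for the difference between 2 binomial proportions". Neither names a covariate or a site term.

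**Primary test.** SAP 8.1.1 specifies an ANCOVA: "Treatment group and analysis site will be included as factors and baseline average SUDS score as a covariate".

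**Role of CGI-I.** SAP 6.1.3: "Testing of the secondary endpoint will proceed only if the primary endpoint achieves statistical significance". No other endpoint is in the sequence. By default, "all statistical tests will be conducted at the 0.05 significance level using 2-tailed tests" (SAP 4.1).

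**What CGI-I measures.** The observer rates the subject's anxiety in the second speech against "how anxious they appeared in the first speech a week ago" (SAP 6.1.7.3). It is a rating of change and has no baseline of its own.

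**Covariate rule.** SAP 6.1.2 has the ANCOVAs adjust for analysis site and for the baseline of the endpoint being analysed. For CGI-I it promises results overall and by stratum. It neither defines the strata nor names a combined test.

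**Randomisation.** SAP 3.5 stratifies by study site only. It requires a completed Visit 2 challenge with at least one SUDS score of 75 or more. On size, "208 subjects (104 in each arm) will be included in the study" (SAP 3.2).

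**The concern.** Baseline average SUDS measures anxiety during the first speech, and CGI-I asks how much less anxious the subject was in the second speech than in that one. Baseline SUDS is therefore a plausible predictor of response. It is recorded before randomisation and should exist for every subject who meets the entry rule. Site is the randomisation stratum. Both are in the primary model and neither is in the CGI-I test.

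What is at stake is efficiency in the only other confirmatory comparison. If either variable predicts response, the planned interval is wider and the test weaker than the collected data allow. If neither does, nothing is lost.

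**Working it through.** **Inputs from the documents.** 104 per arm; two-sided 0.05; Phase 2 CGI-I responders 34/45 (75.6%) versus 17/46 (37%), Z = 4.03 (Protocol 5.2.2).

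**Assumptions.** (a) Responder rates of 55% versus 37%; the readable text gives no design rates or power for CGI-I. (b) R², the share of within-arm response variance explained by baseline SUDS. The documents give no value, so a range is shown.

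**Step 1: reproduce the Phase 2 statistic.** Unpooled SE = √(0.756×0.244/45 + 0.370×0.630/46) = 0.0958. Z = 0.386/0.0958 = 4.03, as the protocol states.

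**Step 2: planned test at 104 per arm.** SE = √((0.55×0.45 + 0.37×0.63)/104) = 0.0680. Power = Φ(0.18/0.0680 − 1.96) = 75.4%. The 95% CI half-width is 1.96×0.0680 = 13.3 percentage points.

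**Step 3: with adjustment.** In large samples, adjusted SE = SE×√(1−R²).

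| R² | Power | CI half-width (points) |
|---|---|---|
| 0 | 75.4% | 13.3 |
| 1% | 75.8% | 13.3 |
| 2% | 76.3% | 13.2 |
| 5% | 77.5% | 13.0 |
| 10% | 79.7% | 12.6 |
| 20% | 84.1% | 11.9 |

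In sample-size terms, R² of 5% is worth 104/0.95 = 109.5 per arm and 10% is worth 104/0.90 = 115.6. At 50% versus 37%, power goes from 48% to 50%, 52% and 57% at R² of 5%, 10% and 20%.

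**Step 4: how strong an association this needs.** With a logistic model and 37% responders, R² of 5% needs an odds ratio of about 1.6 per SD of baseline SUDS. R² of 10% needs about 2.1, and 20% about 3.1.

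**Step 5: simulation check.** The formula ignores the cost of estimating the covariate effect. Simulating 8,000 trials per setting (55% versus 37%, logistic standardisation, influence-function SE) gave:

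| R² | Unadjusted power | Adjusted power |
|---|---|---|
| 0 | 77.0% | 76.0% |
| about 1.5% | 76.2% | 76.1% |
| about 4.5% | 76.0% | 77.3% |
| about 10% | 76.0% | 79.1% |
| about 18% | 76.7% | 83.0% |

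A second set (56% versus 37%, 6,000 trials each) agreed: 80.0% versus 78.4% at R² of 0, and 80.3% versus 82.5% at 9.5%. In that set type I error was 4.7–5.1% unadjusted and 4.5–5.5% adjusted. In the first set the ranges were 5.1–5.6% and 5.1–5.7%.

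**Step 6: at the Phase 2 rates.** SE = √((0.756×0.244 + 0.370×0.630)/104) = 0.0634, and 0.386/0.0634 − 1.96 = 4.1. Power exceeds 99.9% without adjustment.

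These figures cover baseline SUDS only. The effect of adding site terms was not computed.

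**The case against.** The strongest objection is that the benefit is unproven. No readable passage links baseline SUDS to CGI-I response.

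- A reader might infer from "baseline average SUDS score as a covariate" in the primary model that the plan already treats baseline SUDS as prognostic for CGI-I. It does not. SAP 6.1.2 ties that adjustment to the endpoint's own baseline. There, self-rated change is regressed on the same self-rated scale. CGI-I is an observer's dichotomised impression, and prognostic value on one scale need not carry over to the other.
- The 75-point entry rule narrows the spread of baseline SUDS, which makes a large R² less likely. The gain may be negligible.
- A reader might infer that the planned test is biased because chance baseline imbalance stays in the estimate. That is also unsupported. Under randomisation the interval already allows for such imbalance, and simulated type I error is close to 5%.
- A reader might infer that the simple test saves nothing. It does: it needs no model, matches the estimand's comparison of binomial proportions directly, and avoids a small power loss when the covariate is uninformative.
- CGI-I is tested only after success on the primary endpoint, so the power figures here are not the probability of a confirmatory CGI-I claim.

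All of this stands, and it limits the point to a conditional one. It does not remove the point. The likely cost of adjusting is small, the estimand can be kept, and the site omission is plain in the text whatever the value of R².

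**Conclusion.** The planned CGI-I test is valid, and the documents contain no error or contradiction that adjustment would cure. The point is an optional efficiency gain in the only confirmatory comparison after the primary. Its size depends wholly on an R² that the documents do not give. Under the assumed 55% versus 37%, the gain runs from nothing to about 4 points of power for R² up to 10%. Larger gains would need an association that nothing in the documents supports. The downside, if baseline SUDS is not prognostic, is about 1–1.5 points. If the Phase 2 effect is real and full-sized, the choice makes no practical difference to power.

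**What to change.** Before any unblinded analysis, including the interim analysis in Protocol 13.1.6, make these changes to SAP 8.2.1:

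- Fit a logistic model for CGI-I response (score 1 or 2) with treatment, baseline average SUDS and analysis site as pooled under SAP 6.1.6.
- Standardise over all analysed subjects to the marginal difference in proportions, and take the 95% CI and P value from a robust or bootstrap SE. The hypothesis and the difference-in-proportions estimand stay as they are; an odds ratio should not replace them.
- State a fallback in case small sites stop the logistic model from fitting.
- Keep the unadjusted Wald comparison as a supportive result.
- Align Protocol 13.1.4.3, and say in SAP 6.1.2 what the strata are.

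**Cost.** A few sentences in the SAP, some programming and no new data. The SAP is written to protocol Version 3.0 and plans no interim analysis, while the current protocol does, so the SAP needs updating in any case. Changing the protocol line is heavier, because Protocol 14.8 requires investigator signature and IRB approval for an amendment. The method is also slightly harder to explain than a raw comparison, and a small power loss is possible if the covariates are not prognostic.
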